9.5 Analysis Populations

The analysis of the primary endpoint will be based on the Intent-To-Treat (ITT) and Per Protocol (PP) analysis populations in order to support a conclusion of non-inferiority. The inclusion of both ITT and PP populations has been chosen to assess the robustness of the study results and the consistency of the study measures under different analysis populations.

This study has a non-inferiority design; therefore, the primary analysis will be based on the PP population.

For cases in which the ITT and PP populations lead to the same conclusions and final interpretations about the LP MAP effect, the results will be considered to not be influenced by underlying factors such as missing data and protocol deviations, and the results would be considered to be robust and consistent under different analysis populations. A statement to reflect this will be included in the CIR.

For cases in which the ITT and PP populations lead to different final interpretations or conclusions, all of the results will be reported and the differences in outcomes will be identified and explored.

Intent-to-Treat Population

The Intent-to-Treat Population will include all subjects who receive the MAPs and have at least one set of paired MAPs measurements from any endpoint, regardless of protocol deviations and missing data.

Per Protocol Population

The Per Protocol Population will include all subjects who receive the MAPs and have at least one set of paired MAPs measurements without major protocol deviations from any endpoint. Major deviations will be defined and documented at the clean file meeting before data base lock.

It is possible that a LP MAPs has not been administered in the intended counterbalanced order of presentation. It is also expected that the sequence and period effects are minimal in this study if any. This study is not a full cross-over design, so period and sequence effects will not be assessed, without the consequence to bias the study conclusion.

Safety Population

The Safety Population will include all subjects who used the investigational MAPs. The Safety Population will be used for the safety data analysis.

CIP Number: CLTD5853

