3 SCHEDULE OF EVENTS

Visit Type	Screening	Visit 1 ^b	Visit 2	Visit 3	Additional visits ^c	EOSd
Timing of Investigation		Day 0	Week 4	Week 8	NA	NA
Visit window (±)	NA	NA	Min 4 weeks	Min 4 weeks	NA	NA
Procedures						
Written informed consent	X					
Demographics	X					
Eligibility	X					
Hearing history	X					
Device history	X					
Medical history	X					
Mapping		X				
Speech perception testing – Words in Quiet (CNC words at 60dB)	Xa		X	X	Xc	
Speech perception testing – Sentences in Noise (AuSTIN sentences)			X	X	Xc	
Switching acceptability rating (SAR)			Х	Х	Χc	
SSQ12 Questionnaire			X	Х	Xc	

Clinician log		Х				
Concomitant medications/therapies	х	X	Х	Х	X	х
Adverse Events		Х	X	Х	Х	х
Device Deficiencies		Х	X	Х	Х	х
Device exposure		Х	X	Х	Х	Х

^a To be completed if historical records for CNC words (60dB) is not available to assess eligibility

^b Visit 1 can be conducted on the same day as screening

^cOptional; to be conducted if predefined visit procedures could not be completed for any reason

^d End of study (EOS) may be conducted on same day as visit 3 or on an additional visit.

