7.2.7 Randomisation Procedures

Subjects will be randomly allocated to one of four groups. Programming of sound processors for take home use and test order during visits 2 and 3 will be performed as per the randomisation table (Table 4).

Table 4: Randomisation table

	Take home programs	Visit 2 test order	Take home programs	Visit 3 test order
Group 1A	P1: Default	Test 1: Default	P1: LP2	Test 1: LP2
	P2: LP1	Test 2: LP1	P2: LP3	Test 2: LP3
Group 1B	P1: LP1	Test 1: LP1	P1: LP3	Test 1: LP3
	P2: Default	Test 2: Default	P2: LP2	Test 2: LP2
Group 2A	P1: LP2	Test 1: LP2	P1: Default	Test 1: Default
	P2: LP3	Test 2: LP3	P2: LP1	Test 2: LP1
Group 2B	P1: LP3	Test 1: LP3	P1: LP1	Test 1: LP1
	P2: LP2	Test 2: LP2	P2: Default	Test 2: Default

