- Preparation of take-home sound processor: Group 1 will be provided with 900Hz MAPs (Default and LP1), and group 2 will be provided with 500Hz MAPs (LP2 and LP3) as per the randomisation table (Table 4). The SmartSound environments in the frequently used program in their own sound processor will be replicated in the study sound processor with the exception of automatic forward focus (SCAN2FF). Subjects using a SCAN2FF program in their own sound processor will be provided a SCAN2 program with user-controlled ForwardFocus enabled.
- Issue of SSQ12: The SSQ12 questionnaire will be issued, and the subjects will be counselled on how to
 complete the questionnaire as needed. The subjects will be asked to rate their ability to hear speech
 in a variety of competing contexts during their take home period. Subjects are also asked about their
 spatial hearing abilities including the impact of direction, distance and movement associated with
 spatial hearing.

CIP Number: CLTD5853

- Counselling for take home use: Subjects will be asked to switch from program 1 to program 2 on a daily basis so that they acclimate to both programs and to get equal opportunity to use both programs during the take home period. Subjects who typically used the SCAN2FF program prior to enrolment will be asked to use user-controlled ForwardFocus during the take home period.
- **Standard CRFs:** CRFs including concomitant medications, adverse events and device deficiencies will be completed.

Take home use:

- Subjects will be asked to use two MAPs for four weeks. The subjects will be asked to use P1 on day 1, P2 on day 2, P1 on day 3 etc.
- Subjects will be asked to complete the SSQ12 in the fourth week of take home use.

Visit 2:

- Collection of SSQ12:
- Acclimatization: Subjects will be asked to use the specified test MAP for a period of minimum 10 minutes and listen to live or recorded speech to acclimate to two conditions prior to speech perception testing. Contralateral device will be turned off (if applicable).
- **SAR:** The subjects will be asked to provide responses to the questions in the SAR as soon as they have switched to the new MAP at the end of the acclimatisation period.
- CNC word test (60dB): Two lists with 50 words each will be administered per condition. The
 contralateral ear will be plugged. The test order will be determined using the randomisation table (Table
 4)

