9.2.1 Primary Endpoints

- 1) Paired difference in percentage CNC Words correct between default and LP1 MAPs in quiet setting
- 2) Paired difference in dB SRT (AuSTIN) between default and LP1 MAPs in noise

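### Agreement between ITT and PP cannot show that missing data had no influence, because both primary analyses leave out every subject without the default/LP1 pair

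*Combined protocol and SAP*

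**What the plan says.** Section 9.5 makes PP the primary population and runs ITT alongside it. If the two agree, "the results will be considered to not be influenced by underlying factors such as missing data and protocol deviations"; and "A statement to reflect this will be included in the CIR".

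The ITT population is "all subjects who receive the MAPs and have at least one set of paired MAPs measurements from any endpoint", whatever the deviations or missing values. PP subjects must "have at least one set of paired MAPs measurements without major protocol deviations from any endpoint". Neither definition asks for the default/LP1 pair in particular.

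The two primary endpoints (section 9.2.1) are default/LP1 differences: one in CNC words, the other the "Paired difference in dB SRT (AuSTIN) between default and LP1 MAPs in noise". Section 9.6.1 analyses each by the 95% confidence interval of the mean paired difference. Sections 9.1 to 9.8 mention no imputation, no model for incomplete data and no missing-data sensitivity analysis. Section 14.3 requires a final SAP before database lock, but the supplied text contains no further method.

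Under Table 4 (section 7.2.7), groups 1A and 1B are tested on default and LP1 at Visit 2, and groups 2A and 2B at Visit 3. Section 9.4 allows for 25% attrition among 20 enrolled subjects. Sections 7.2.6 and 9.4 allow withdrawn subjects to be replaced.

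**The concern.** Comparing two analyses tells us about a source of bias only if they treat that source differently. ITT and PP treat major deviations differently. They treat an absent primary pair identically, because both leave the subject out. The rule nevertheless turns agreement into a conclusion about missing data.

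If a primary pair is missing, the CIR would state that a non-inferiority result was unaffected by missing data, on evidence that cannot bear on the question. Section 9.6 ties formal testing to labelling claims, so the wording matters.

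The direction of any bias is unknown:

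- Loss linked to a worse LP1-minus-default difference favours a non-inferiority conclusion.
- Loss linked to poor performance with default acts the other way.
- Loss linked only to overall performance, or to LP2 or LP3, does not by itself bias the primary difference.

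ITT/PP agreement cannot tell these cases apart.

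**Working it through.** **1. The plan's own sizing.** Inputs from section 9.4: margins 10 points and 1 dB, SDs of differences 6.914 points and 1.037 dB, one-sided alpha 0.025, n = 14. The true difference is not stated; 0 is assumed. A paired t-test with the noncentral t distribution gives 99.9% power for CNC and 91.5% for SRT, against the stated values of more than 90% and 90%. For SRT, 14 is the smallest n that reaches 90% (n = 13 gives 89.0%). The sizing reproduces, so this point does not rest on a sizing error.

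**2. Who enters each primary analysis.**

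| Subject | In ITT | In PP | In ITT primary mean | In PP primary mean |
|---|---|---|---|---|
| Has default/LP1 pair, no major deviation | yes | yes | yes | yes |
| Has default/LP1 pair, major deviation | yes | no | yes | no |
| Group 2, leaves after Visit 2 with LP2/LP3 pair only, no major deviation | yes | yes | no | no |
| Leaves before any paired test | no | no | no | no |

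Only the second row can separate the two results. The third row shows how set membership hides the gap: the subject counts in both populations and contributes to neither primary mean. Replacement restores the number analysed but does not recover the lost pair.

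**3. How far missing pairs could move the result.** Take 16 completers with mean m (LP1 minus default) and the planned SD s, and add k subjects at a common value v, so N = 16 + k:

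- pooled mean = (16m + kv)/N
- sum of squares SS = 15s² + (16k/N)(v − m)²
- limit on the harmful side = pooled mean ± t(0.975, N−1) × √(SS/(N−1))/√N (plus for SRT, minus for CNC)

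Example: SRT, m = 0, k = 4, v = +1 dB. The mean is 0.20, SS = 15 × 1.037² + 3.2 = 19.33, and the pooled SD is √(19.33/19) = 1.009. The limit is 0.20 + 2.093 × 1.009/√20 = 0.67 dB, still below 1 dB.

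The tipping value is the v at which the limit meets the margin.

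| Endpoint | m (assumed) | Limit, 16 completers | Limit, four added at the margin | Tip, four missing | Tip, two missing | Tip, one missing |
|---|---|---|---|---|---|---|
| SRT, dB | 0 | 0.553 | 0.672 | +2.07 | +2.92 | +4.32 |
| SRT, dB | +0.30 | 0.853 | 0.892 | +1.40 | +1.76 | +2.38 |
| SRT, dB | +0.40 | 0.953 | 0.966 | +1.13 | +1.26 | +1.51 |
| CNC, points | 0 | −3.68 | −5.46 | −23.4 | −33.5 | −49.6 |
| CNC, points | −3 | −6.68 | −7.57 | −17.8 | −24.0 | −34.0 |
| CNC, points | −5 | −8.68 | −9.03 | −13.5 | −16.5 | −21.7 |

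**4. False non-inferiority for SRT.** Simulation: true mean 1 dB, SD 1.037, 16 completers, 200,000 trials. Loss is driven by a latent score with an assumed correlation to the LP1-minus-default difference.

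| Loss scenario | False non-inferiority |
|---|---|
| Unrelated to the difference | about 2.5% |
| 5–10% lost, all linked to a worse difference, correlation 0.1–0.3 | 2.7%–4.1% |
| 20–25% lost, half linked, correlation 0.3–0.5 | 4.1%–6.5% |
| 20–25% lost, all linked, correlation 0.3–0.5 (stress case) | 6.0%–13.0% |
| 20–25% lost, all linked the other way, correlation 0.3–0.5 | 0.3%–0.9% |

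In a separate check, 25% were lost for poor average performance over default and LP1 (between-subject SD assumed to be 1 or 3 dB). The rate stayed at 2.5%, with no shift in the mean difference.

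**The case against.** **Complete-case analysis is inferred.** The plan never says that subjects without the pair are dropped, and the SAP named in section 14.3 might add a method. This is fair as a limit on certainty. Nothing supplied contains such a method, though, and if one is intended, section 9.5 should refer to it.

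**Not all missing data are missing pairs.** Each condition needs two lists of each test, and section 13 treats partly omitted assessments as deviations. A pair built on incomplete lists could be in ITT but not in PP, so the comparison can be informative there. This stands, and a statement limited to protocol deviations still covers that case.

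**Missing pairs are unlikely.** Both conditions of a pair are tested at one visit. Additional visits are available, "to be conducted if predefined visit procedures could not be completed for any reason". Section 7.2.6 requires at least three contact attempts, and subjects can fall back on their own processor (sections 8.2 and 8.4). All this lowers the chance of a missing pair. It does not make the inference valid when one occurs.

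**The effect is small.** This largely stands. The low SRT tipping values need a completer result already near the margin. With a true difference of 0, about 8% of simulated trials of 16 conclude non-inferiority with a mean of +0.30 dB or more, and about 2% with +0.40 dB or more. No document supports any particular correlation, and 25% is an allowance, not a forecast.

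**Some of the reporting is already planned.** Scores are summarised by population (section 9.6.1) and withdrawal reasons recorded where given (section 7.2.6). The new element is a count of missing primary pairs by group.

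**Conclusion.** The concern holds. As written, the rule supports a statement about deviations among subjects with the default/LP1 pair, and none about subjects without it. This rests on the paired-difference estimator and on the absence of any missing-data method in the supplied text.

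The likely numerical consequence is modest. CNC is insensitive at the completer means examined, and SRT could be sensitive only when its result lies close to 1 dB. No bias is demonstrated and its direction is unknown. The estimator, margins, test and decision rule are not in question. What is wrong is the conclusion the CIR is committed to draw if any primary pair is missing.

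**What to change.** In section 9.5:

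1. Take missing data out of the agreement statement and limit it to protocol deviations among subjects who have the default/LP1 pair.
2. Report how many subjects commenced Visit 1 and lack that pair, by randomised group and with reasons where given, counting those who were later replaced. Give the number analysed for each primary endpoint.
3. If a primary pair is missing and a statement of robustness to missing data is wanted, base it on a simple sensitivity analysis, for example a tipping point for both primary endpoints, or cross-refer to one in the SAP. Otherwise make no such statement.

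The cost is one changed sentence, one small table from subject status already held in the CRF (section 14), and at most one short analysis. No new data are collected. The possible downside for the sponsor is a less favourable robustness statement.

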9.4 Sample Size Determination

This study is a non-inferiority design, and sample size calculation was based on non-inferiority tests for CNC word scores and SRT (Speech Recognition Threshold) scores.

To reject the null hypothesis of inferior CNC Words correct in quiet (60 dB) scores, a sample size of 14 will provide more than 90% power to detect non-inferiority of CNC word scores and 90% power to detect non-inferiority of SRT with the following parameters:

CIP Number: CLTD5853

- A clinically important difference value of 10% for CNC words and 1 dB SRT for AuSTIN. This margin is based on clinical consensus.
- A SD of change or difference scores of 6.914% for CNC words and 1.037 dB for AuSTIN. The expected standard deviation of difference scores for CNC words was based on a previous dual electrode mode study (CRC 5523) on the relevant endpoints.
- A significance level $\alpha = 0.025$ (one-tailed).

There are four subgroups in the randomisation table (Table 4); to ensure equal number of subjects in each subgroup a minimum of sample size of 16 (or a higher multiple of 4) is required. Twenty subjects will be enrolled in total to allow for any unforeseen subject withdrawal with a possible attrition rate of 25% and to ensure equal number of subjects in the four subgroups. Replaced subjects will be recruited if the minimum sample size of 16 could not be met due to subject withdrawal or loss to follow up.

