9.6 Endpoint Analyses

For all hypothesis testing to be performed on primary and secondary endpoints, the overall type I error rate will be maintained via a gatekeeping approach whereby statistical tests will proceed in order as stated under the section 9.3 until a non-significant test is obtained, at which point, formal testing for the purposes of labelling claims will cease. However, summary statistics on the remaining endpoints will still be performed.

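### A per-protocol pass can open the testing gate and support a labelling claim while ITT fails, because agreement is not required and the gate names no population

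*Combined protocol and SAP*

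**What the plan says.** Section 9.5 begins by basing the primary-endpoint analysis on both ITT and PP as support for a non-inferiority conclusion, and gives robustness as the reason for having two sets. It then ranks them: "This study has a non-inferiority design; therefore, the primary analysis will be based on the PP population". If the two sets lead to the same conclusion, the result is called robust. If they differ, "all of the results will be reported and the differences in outcomes will be identified and explored".

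Section 9.6 sets a fixed sequence for the primary and secondary hypotheses: "statistical tests will proceed in order as stated under the section 9.3 until a non-significant test is obtained". At that point formal testing for labelling claims ends. Six hypotheses pass through this gate: primary endpoints 1-2 and secondary endpoints 1-4.

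The confidence-interval criteria in sections 9.3 and 9.6.1 (CNC lower limit above -10%, SRT upper limit below 1 dB) name no population. Section 9.6.2 sends the secondary tests back to 9.6.1. Section 9.5 speaks only of the primary endpoint when it assigns populations.

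**The concern.** The gate needs one pass-or-fail verdict per hypothesis. The natural reading is that PP supplies it, since PP is primary and reporting a disagreement changes nothing. A measure could then be claimed, and the next one tested, while the interval in all analysable subjects crosses the margin. That fits poorly with the statement in 9.5 that both sets support the conclusion.

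It would matter little if leaving PP had nothing to do with outcome, but the plan gives reasons to doubt that:

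- Major deviations are defined only at the clean file meeting, after data collection (section 9.5).
- Investigators are not blinded (section 7.1.1) and are sponsor employees (section 7.5).
- Section 5.1 has subjects using the study MAPs exclusively, while section 8.4 lets them return to their own programs when performance is insufficient. The plan does not say whether doing so is a major deviation. If it is, subjects who do badly on a low-power MAP could stay in ITT and leave PP.

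**Working it through.** **Inputs from section 9.4.** Margins: "A clinically important difference value of 10% for CNC words and 1 dB SRT for AuSTIN". Spread: "A SD of change or difference scores of 6.914% for CNC words and 1.037 dB for AuSTIN". One-sided alpha 0.025; 20 subjects enrolled; 25% attrition allowed for. The documents give no true difference, no number of PP exclusions and no outcome for excluded subjects, so these are assumptions. A paired t interval is also assumed.

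**Step 1. Reproduce the plan's power.** Section 9.4 states that "a sample size of 14 will provide more than 90% power to detect non-inferiority of CNC word scores and 90% power to detect non-inferiority"; the second figure is for SRT. For a paired t test with true difference 0, power = P(T > t(0.975, n-1)), where T is noncentral t with noncentrality (margin/SD) × √n.

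- SRT, n = 14: noncentrality (1/1.037) × √14 = 3.61, power 91.5%. At n = 13 it is 89.0%, so 14 is the smallest n that reaches 90%.
- CNC, n = 14: noncentrality (10/6.914) × √14 = 5.41, power 99.9%.

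The stated figures hold.

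**Step 2. Can PP pass while ITT fails?** Take invented SRT data.

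- PP: n = 16, mean +0.30 dB, SD 1.037. Upper limit = 0.30 + 2.131 × 1.037/√16 = 0.85 dB, a pass.
- Add 4 excluded subjects with mean +1.5 dB and the same SD. ITT mean = (16 × 0.30 + 4 × 1.5)/20 = 0.54. The sum of squares is 18 × 1.037² + 16 × 0.24² + 4 × 0.96² = 23.96, so SD = √(23.96/19) = 1.12. Upper limit = 0.54 + 2.093 × 1.12/√20 = 1.07 dB, a fail.

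**Step 3. Exclusions unrelated to outcome.** Simulate normal differences with SD 1.037, ITT n = 20 and PP a subset. With a true loss of 1 dB in everyone, PP alone passes in 2.5% of trials at PP n = 16 or 18; both sets pass in 1.4% and 1.7%. With true difference 0 in everyone, PP passes and ITT fails in about 0.3% of trials.

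**Step 4. Informative exclusions.** Hold the all-subject mean loss at exactly 1 dB and let k excluded subjects lose d dB. The PP mean is then (20 - k × d)/(20 - k).

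| PP n | d (dB) | Implied PP mean (dB) | PP alone passes | Both pass |
|---|---|---|---|---|
| 16 | 2.0 | 0.75 | 14.6% | 1.4% |
| 16 | 2.5 | 0.63 | 27.3% | 0.8% |
| 17 | 2.0 | 0.82 | 9.7% | 1.7% |
| 17 | 2.5 | 0.74 | 16.6% | 1.1% |
| 18 | 2.0 | 0.89 | 6.3% | 1.9% |
| 18 | 2.5 | 0.83 | 9.4% | 1.5% |

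**Step 5. Price of requiring both (SRT power, true PP difference 0).**

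| ITT n / PP n | Excluded subjects' mean loss | PP alone | Both | Points lost |
|---|---|---|---|---|
| 20 / 16 | 0 dB | 95.0% | 94.7% | 0.3 |
| 20 / 18 | 0 dB | 97.0% | 96.8% | 0.2 |
| 15 / 13 | 0 dB | 89.0% | 88.1% | 0.9 |
| 20 / 18 | 2.0 dB | 97.0% | 83.5% | 13.5 |
| 20 / 18 | 2.5 dB | 97.0% | 73.0% | 24.0 |
| 20 / 16 | 2.0 dB | 95.0% | 48.1% | 46.9 |
| 20 / 16 | 2.5 dB | 95.0% | 24.1% | 70.9 |

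ITT n = 15 is 20 less 25%. In the last four rows the true all-subject mean is only 0.2 to 0.5 dB (for example 4 × 2.5/20 = 0.5), so non-inferiority is true in both sets. CNC power with no true difference stays above 99.9%.

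**The case against.** The best defence is that section 9.5 describes a primary analysis with a sensitivity analysis beside it. PP is named primary, 9.6.1 gives the criterion, and together they yield one verdict. Disagreement must be reported, so an ITT failure cannot be hidden. Much of this stands, and it rules out three stronger readings:

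- *The plan has no decision rule.* Naming PP as primary is a default rule. What is missing is any effect of ITT on the verdict and a named population for the gate.
- *Type I error control is undefined.* It is not. PP alone holds 2.5% when exclusions are unrelated to outcome (step 3).
- *The 6% to 27% are false claims outright.* In step 4 the true PP mean lies inside the margin, so for the PP population these passes are power. They are errors only if the all-subject mean is the target.

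The two sets may also differ little. Both need a paired measurement, so subjects who drop out without one leave both, and the PP definition can be read as needing only one clean pair. Section 14.3 refers to a final SAP, and a separate one might hold the rule; none is in the supplied text.

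None of this gives ITT a role in the verdict or assigns a population to the secondary tests. Reporting a disagreement does not close the gate.

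**Conclusion.** The point holds as a gap in the success criterion. Under the current text a PP pass with an ITT fail can carry the sequence forward and support a labelling claim. That PP drives the gate is an inference from its designation as primary, since section 9.6 does not say so.

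The size depends on why subjects leave PP. If exclusions are unrelated to outcome, the consequence is negligible. If 2 to 4 of 20 leave PP with a 2.0 to 2.5 dB loss, and the all-subject mean loss is exactly 1 dB, PP alone succeeds several times more often than the nominal 2.5%, measured against that all-subject mean. The exclusion counts and losses are assumptions without a source in the documents. The late definition of major deviations and the unblinded investigators make informative exclusion plausible; they do not show that it will occur.

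**What to change.** Add to sections 9.5 and 9.6, before any data are reviewed:

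> For primary endpoints 1-2 and secondary endpoints 1-4, non-inferiority is concluded, and testing proceeds to the next hypothesis, only if the 95% CI clears the margin in both the PP and the ITT populations. Otherwise the test counts as non-significant.

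This uses two populations that the plan already defines and needs no extra subjects. The power cost is small when excluded subjects do not differ: 0.2 to 0.3 points at ITT n = 20, about 0.9 points at ITT n = 15 with PP n = 13. It is large, between 13 and 71 points in step 5, if excluded subjects really lose 2.0 to 2.5 dB. The sponsor should accept that knowingly: it is also the situation in which a PP-only claim is least secure.

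If the sponsor means PP alone to decide, the plan should say so for each of the six tests and define major deviations before data are seen, including whether reverting to own programs counts.

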- AuSTIN sentence test: Both recorded speech and noise (adaptive four talker babble noise) will be presented from 0 degrees azimuth (S0N0). The signal level will be fixed at 65 dB SPL. One practice list will be administered at the beginning of the session to overcome learning effects. Two lists with 20 sentences each will be administered per condition. If the standard deviation (SD) for any list exceeds 4.12, then the run will be considered as invalid and additional list will be administered. The contralateral ear will be plugged.
- Loading MAPs to processors: CDI Tool will be used to load the test MAPs into a study sound processor for take home use as per the randomisation table (Table 4).
- **Issue of SSQ12:** The SSQ12 questionnaire will be issued, and the subjects will be counselled on how to complete the questionnaire as needed.
- **Standard CRFs:** CRFs including concomitant medications, adverse events, device deficiencies and device exposure will be completed.

CIP Number: CLTD5853

Take home use:

- Subjects will be asked to use two MAPs for four weeks. The subjects will be asked to use P1 on day 1,
 P2 on day 2, P1 on day 3 etc.
- Subjects will be asked to complete the SSQ12 in the fourth week of take home use.

Visit 3:

- Collection of SSQ12:
- Acclimatization: Subjects will be asked to use the specified test MAP for a period of minimum 10
 minutes and listen to live or recorded speech to acclimate to the two conditions prior to speech
 perception testing. Contralateral device will be turned off (if applicable).
- **SAR:** The subjects will be asked to provide responses to the questions in the SAR as soon as they have switched to the new MAP at the end of the acclimatisation period.
- **CNC word test (60dB):** Two lists with 50 words each will be administered per condition. The contralateral ear will be plugged. The test order will be determined using the randomisation table (Table 4)
- AuSTIN sentence test: Both recorded speech and noise (adaptive four talker babble noise) will be
 presented from 0 degrees azimuth (S0N0). The signal level will be fixed at 65 dB SPL. One practice list
 will be administered at the beginning of the session to overcome learning effects. Two lists with 20
 sentences each will be administered per condition. If the SD for any list exceeds 4.12, then the run will
 be considered as invalid and additional list will be administered. The contralateral ear will be plugged.

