9.3 Hypotheses

For the non-inferiority test of CNC words, the 95% CI (alpha=0.025 one-sided) for the mean paired difference will be estimated. If the lower limit of the 95% CI of the mean paired difference is above -10%, the treatment condition is regarded as non-inferior to the control on that measure.

For the non-inferiority test of SRT sentences for both primary and secondary endpoints, the 95% CI (alpha=0.025 one-sided) for the mean paired difference will be calculated. If the upper limit of the 95% CI of the mean paired difference is lower than 1dB, the treatment condition is regarded as non-inferior to the control on that measure.

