13 DEVIATIONS FROM THE CLINICAL INVESTIGATION PLAN

The Investigator(s) must not deviate from the CIP, except in case of an emergency to protect the safety and well-being of the subject(s). Such deviations will be documented by the site personnel in the source documentation for the subject and reported to the relevant EC as per institutional requirements and to the Sponsor as soon as possible, but not later than 5 working days from the date of the emergency.

If there is a deviation from CIP-defined assessments or parts thereof are omitted or completed incorrectly, the deviation will also be documented by the site personnel in the source documentation for the subject. Depending on the type or severity of the deviation the Investigator may be required to notify the EC, particularly if the deviation potentially impacts subject safety, performance of IMD and/or comparator, or data integrity.

All CIP deviations will be documented in the eCRF to enable analysis and reporting by the Sponsor in the Clinical Investigation Report (CIR), or to the relevant regulatory authority(s), if applicable.

Gross misconduct on behalf of an Investigator, such as intentional non-compliance with CIP or GCP requirements or fraud, will result in disqualification of the Principal Investigator and/or Investigational Site from participation in the investigation. Data provided by the Principal Investigator or Investigational Site will be excluded from the per-protocol analysis group.

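### Per Protocol membership is set once per subject by one clean pair on any endpoint, and no written rule removes a default/LP1 pair with a major deviation from the primary analysis

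*Combined protocol and SAP*

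**What the plan says.** Section 9.5 makes PP the primary set: the study is a non-inferiority design, "therefore, the primary analysis will be based on the PP population". A subject who received the MAPs enters PP with "at least one set of paired MAPs measurements without major protocol deviations from any endpoint". The ITT sentence is built the same way and asks for "at least one set of paired MAPs measurements from any endpoint, regardless of protocol deviations and missing data".

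Section 9.5 also says how the two sets will be used together. If they lead to the same conclusion, the results will be taken as uninfluenced by missing data and protocol deviations, and the investigation report will say so.

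On deviations, section 9.5 adds only this: "Major deviations will be defined and documented at the clean file meeting before data base lock". Sections 9.6 and 9.6.1 set out the testing order and the confidence-limit rule, and neither excludes data for a particular endpoint.

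**The concern.** A PP set does its work in a non-inferiority trial by keeping compromised measurements out of the comparison being tested. Here the entry test looks at whether the subject has a clean pair somewhere. It does not ask whether the default/LP1 pair is clean.

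The design makes the difference matter. Under Table 4 (section 7.2.7), default and LP1 are tested at one visit and LP2 and LP3 at the other. Suppose the wrong MAP is loaded or tested at the default/LP1 visit. The LP2/LP3 pairs, which are exploratory endpoints in section 9.2.3, can still be clean and are enough to admit the subject. A fault confined to the CNC test would likewise leave the AuSTIN pair from the same visit to qualify the subject.

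Two things are at stake. First, the primary test may include pairs that the plan itself would class as having a major deviation. Second, those pairs sit in ITT as well, so agreement between the sets says nothing about their influence. The planned robustness statement rests on that agreement.

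**Working it through.** **Step 1. Which reading of the definition fits.** The PP and ITT sentences share the requirement of at least one set of paired measurements from any endpoint. In the ITT sentence, the reference to any endpoint can only say where the pair may come from. Read in parallel, the PP sentence means one clean pair, from whichever endpoint. The alternative, no major deviation on any endpoint, fits poorly with a requirement for at least one set.

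**Step 2. Whether another rule removes the pair.**

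- Section 9.5, clean file meeting: decides which deviations are major. It does not say which measurements are then dropped.
- Section 13: "Data provided by the Principal Investigator or Investigational Site will be excluded from the per-protocol analysis group". This applies only to gross misconduct.
- Section 7.3.2, AuSTIN: "If the standard deviation (SD) for any list exceeds 4.12, then the run will be considered as invalid and additional list will be administered". This is a variability check on a list. It would not detect a wrong MAP, and CNC has no equivalent.
- Sections 9.6 and 9.6.1: no endpoint-level exclusion.

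None of these covers a major deviation on a default/LP1 pair.

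**Step 3. Reproducing the plan's sample size.** Inputs from sections 9.3 and 9.4: margins of 10% (CNC) and 1 dB (SRT), SDs of paired differences of 6.914% and 1.037 dB, one-sided alpha 0.025. The documents give no true difference, so zero is assumed. Power of the paired non-inferiority t-test is 1 − F(t(0.975, n−1)), where F is the noncentral t distribution with n−1 degrees of freedom and noncentrality (margin/SD)·√n.

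- SRT, n = 14: noncentrality (1/1.037)·√14 = 3.61, critical value 2.16, power 91.5%. At n = 13 power is 89.0%, so 14 is the smallest n reaching 90%.
- CNC, n = 14: noncentrality (10/6.914)·√14 = 5.41, power 99.9%.

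The plan's 14 is reproduced.

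**Step 4. False non-inferiority with deviating pairs retained.** Assumptions that are not in the documents: 16 pairs analysed (the section 9.4 minimum), k of them deviating, and all other pairs with a true difference exactly at the margin. Each simulated trial applies the section 9.3 rule: "the 95% CI (alpha=0.025 one-sided) for the mean paired difference will be estimated" and compared with the margin. Writing the difference so that positive is worse for LP1, non-inferiority is declared when mean + t(0.975, 15)·s/√16 is below the margin. The rates are simulated, and independent runs agree to about 0.1 percentage point.

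| True mean in deviating pairs | SRT, k = 1 / 2 / 3 | CNC, k = 1 / 2 / 3 |
|---|---|---|
| Zero (for example, the same MAP tested twice) | 3.7 / 5.5 / 7.8% | 4.1 / 6.9 / 10.8% |
| Half the margin | 3.2 / 3.9 / 4.9% | 3.4 / 4.7 / 6.3% |
| At the margin, SD doubled | about 2.4% | about 2.4% |
| 1.5 times the margin (LP1 made worse) | 1.9 / 1.4 / 1.0% | 1.6 / 0.9 / 0.6% |

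With k = 0 the rate is the nominal 2.5%. Each figure is for one test taken alone. Under the fixed order in section 9.6, SRT is formally tested only after CNC has passed.

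**Step 5. Power if deviating pairs are removed.** The Step 3 formula, starting from 16 completers:

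| Pairs removed | n | SRT power | CNC power |
|---|---|---|---|
| 0 | 16 | 95.0% | >99.9% |
| 1 | 15 | 93.4% | 99.9% |
| 2 | 14 | 91.5% | 99.9% |
| 3 | 13 | 89.0% | 99.7% |
| 4 | 12 | 86.0% | 99.5% |

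**The case against.** The strongest reply is that section 9.5 says who belongs to the PP set and is silent on which of a member's measurements are analysed. The phrase about major deviations qualifies the pair and not the subject, which is compatible with analysing clean pairs only. Section 14.3 also requires a final SAP and a completed clean file meeting before lock, and either could supply the missing rule. This stands to the extent that one cannot say the compromised pair will be kept. One can say only that no written rule takes it out. It does not cure the definition, because a rule chosen once deviations are known is easier to challenge than one fixed in the plan.

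A reader might infer that PP and ITT hold the same primary pairs, so that their agreement is automatic. The documents do not support that. A deviation affecting the whole subject leaves no clean pair, and the subject then leaves PP but stays in ITT. An eligibility breach, or a fault in creating the four MAPs at Visit 1, would do this if classed as major. The gap concerns deviations confined to some pairs.

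Some test-level faults are already limited by the AuSTIN repeat rule and by the additional visits allowed for incomplete procedures. Neither reaches every deviation.

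The error rates depend on an assumed number and type of deviation, for which the plan gives no figures. A reader might also infer that retained deviations always favour non-inferiority. Step 4 shows that they do not: added noise leaves the rate near nominal, and deviations that worsen LP1 lower it. Nor does section 9.5 give shrinkage of differences as its reason for making PP primary; it cites only the non-inferiority design.

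**Conclusion.** The point holds as a fault in the PP definition. Followed as written, the rule can leave default/LP1 pairs with major deviations in the primary analysis and in both analysis sets. ITT/PP agreement would then not support the planned statement that deviations did not influence the results. That conclusion follows from the text and does not depend on the direction of bias. The check is weakened, not empty.

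The effect on error is conditional. With 16 pairs, the protocol's SDs, one to three deviating pairs and the rest at the margin, false non-inferiority goes from 2.5% to about 3.7–7.8% (SRT) and 4.1–10.8% (CNC) if the deviating pairs truly average zero. If the difference is only halved, it goes to about 3.2–4.9% and 3.4–6.3%. It falls below 2.5% if deviations worsen LP1. These figures show what could happen and do not forecast this trial. The sample size itself is sound. The definition should be corrected before database lock.

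**What to change.** In section 9.5, replace the PP entry rule with: *A subject is included in the PP analysis of an endpoint only if both MAP measurements forming that paired difference were obtained without a major protocol deviation.* Carry the same sentence into the separate SAP.

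Leave the ITT rule as it is, with all available pairs analysed regardless of deviations. Applying the same exclusion to ITT would contradict its definition and remove the contrast that the robustness check needs.

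The cost is one sentence and a PP n that may be slightly smaller for some endpoints. By Step 5, the planned size absorbs the loss of two pairs from 16 completers, or six from 20 (n = 14 either way), with SRT power still at 91.5%. A third pair lost from 16 takes it to 89.0%. CNC power stays above 99% throughout.
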